2.2.3 Exploratory endpoints

 TTD is defined as the time from the randomization to treatment discontinuation for any reason (including progression of disease, treatment toxicity, refusal, lost to follow-up and death). Censoring for TTD (patients on treatment or completed treatment), will occur at the last-follow-up date

 DoR is defined as the time from the documentation of tumour response (either partial or complete response) to disease progression or death. Censoring will occur at the last tumour assessment with response other than progression.

2.2.4 (Serious) Adverse Events

Adverse Events (AEs)

The main criterion for treatment tolerability is the occurrence of toxicities and adverse events. The severity and causality will be classified according to the NCI CTCAE version 4 (http://evs.nci.nih.gov/ftp1/CTCAE/About.html).

An adverse event is defined as any untoward medical occurrence that occurs from the day of enrolment in the Remote Data Entry (RDE) until 100 days after the final dose of IMP regardless of whether it is considered related to a medication. The relation of the adverse event with the administered trial treatment has to be indicated as: unrelated, unlikely, possible, probable or definite. In addition, any known untoward event that occurs subsequent to the adverse event reporting period that the investigator assesses as possibly related to the protocol treatment should be considered an adverse event.

Immune-related Adverse Events (irAEs)

The following adverse events are of special interest and must be documented after randomization in both treatment arms:

CTCAE Version 4.0 system organ class / preferred terms:

Nervous system disorders:

- Peripheral motor neuropathy
- Peripheral sensory neuropathy
- Meningismus
- Limbic Encephalitis
- Nervous system disorders Other, specify (Guillain-Barré, myasthenia gravis, aseptic or non-infectious meningitis)

Skin and subcutaneous tissue disorders:

- Stevens-Johnson syndrome
- Toxic epidermal necrolysis
- Bullous dermatitis
- Rash acneiform
- Rash maculo-papular
- Pruritus
- Skin and subcutaneous tissue disorders Other, specify

Gastrointestinal disorders:

- Colitis

- Diarrhea
- Colonic perforation
- Small intestinal perforation
- Gastric perforation
- Gastrointestinal disorders Other, specify

Hepatobiliary disorders:

- Hepatic failure
- Hepatitis viral
- Drug-induced liver injury (DILI)

Investigations:

- Alanine aminotransferase increased
- Aspartate aminotransferase increased
- Blood bilirubin increased

Endocrine:

- Adrenal insufficiency
- Hypothyroidism
- Endocrine disorders Other, specify (hypopituitarism, hypophysitis)

Respiratory, thoracic and mediastinal disorders:

Pneumonitis

Renal and urinary disorders:

- Renal and urinary disorders - Other, specify (nephritis)

Eye disorders:

- Uveitis
- Eye disorders Other, specify (iritis)

Blood and lymphatic system disorders:

- Blood and lymphatic system disorders- Other, specify (haemolytic anaemia)

Cardiac disorders:

Myocarditis

Serious Adverse Events (SAEs)

An SAE is defined in general as any undesirable medical occurrence/adverse drug experience that occurs during or within 100 days after stopping study treatment that, at any dose, results in any of the following:

- is fatal (any cause)
- life-threatening,
- requires or prolongs inpatient hospitalization,
- results in persistent or significant disability/incapacity
- is a congenital anomaly or birth defect
- is a secondary malignancy
- is a medically important event
- overdose (although this event is not always serious by regulatory definition, overdose must be handled as SAE)

- pregnancy

Second (non-SCLC) malignancies are always considered SAEs, no matter when they are diagnosed. Other significant/important medical events which may jeopardize the patient are also considered SAEs. Serious also includes any other event that the investigator or the ETOP Safety Office judges to be serious or which is defined as serious by the regulatory agency in the country in which the event occurred.

Severity Grade

The adverse event severity grade provides a qualitative assessment of the extent or intensity of an adverse event, as determined by the investigator or as reported by the patients. *The severity grade does not reflect the clinical seriousness of the event*, only the degree or extent of the affliction or occurrence (e.g. severe nausea, mild seizure), and does not reflect the relationship to study drug.

Severity grade for other adverse events not covered in the toxicity grading scale:

Grade 1	Mild- transient or mild discomfort; no limitation in activity; no medical intervention/therapy required
Grade 2	Moderate- mild to tolerate limitation in activity; some assistance may be needed; no or minimal medical intervention/therapy required
Grade 3	Severe- marked limitation in activity, some assistance usually required; medical intervention/therapy required, hospitalization is possible
Grade 4	Life-threatening- extreme limitation in activity, significant assistance required; significant medical intervention/therapy required, hospitalization or hospice care probable
Grade 5	Fatal- the event results in death

2.3 Analysis population

Efficacy cohort: The efficacy cohort is the Intention-to-treat (ITT) population of the trial and includes all randomized subjects under protocol AM1. Patients will be evaluated in the treatment arms to which they were randomly assigned, regardless of the treatment actually received, including patients who were randomized but did not receive any trial treatment.

Safety cohort: The safety cohort consists of all subjects who have received at least one dose of IMP treatment plus all patients randomized to observation arm (under protocol AM1).

Patients will be evaluated according to the treatment they actually received, irrespective of their allocated treatment at randomization.

Per-Protocol cohort: Per-protocol cohort includes all patients enrolled under protocol AM1.

Per-Protocol safety cohort: Per-protocol safety cohort includes all patients enrolled under protocol AM1, who received at least one dose of chemo-radiotherapy after enrollment.

3 Primary efficacy analysis of PFS

Primary efficacy analysis of PFS (primary endpoint) will be performed on **all randomized patients under AM1 protocol, based on their initial treatment assignment (ITT, efficacy cohort)**. PFS time is measured from time of randomization.

Formal hypothesis testing

Based on the protocol AM1 and after the modifications arose from the premature study accrual termination, the trial is designed to test the hypotheses that treatment with chemoradiotherapy and PCI followed by consolidation treatment (nivolumab plus ipilimumab) will lead to an increase in median PFS to 22.8 months, from 13.1 months under treatment with chemoradiotherapy and PCI without consolidation treatment. According to the study design, this corresponds to a PFS HR of 0.57. Using 80% power and a one-sided type I error of 5%, a total of 81 PFS events are needed to observed in order to achieve the trial goal.

In the frame of final efficacy analysis, the **formal comparison** of the PFS between the two treatment arms, will be based on **stratified log-rank test** (with number of fractions of radiotherapy [1/2] and administration of FDG-PET-CT [Yes/No] being the stratification factors). Unstratified log-rank test will be also calculated. This would be of particular value in case at least one stratum level has very low number of patients.

Further PFS analyses

The following **PFS analyses** will also be performed and presented

- The total number (%) of PFS events observed, overall and by treatment arm will be presented. In addition, 6-month and 1/2-year PFS estimates, median PFS and respective 95% CI will be provided. Respective results by stratifications factors will be also presented.
- Kaplan-Meier plots by treatment arm as well as by treatment arm within each stratification factor will be created.
- Number of PFS events, median PFS and unstratified/unadjusted HRs (along with 95% CI) will be summarized for the **subgroups** defined by the following clinicopathological variables of interest: gender, smoking history, ECOG performance status at randomization, stage of tumour, age (appropriately categorized) and biological markers (if available). This information will be depicted in a tabular format in the report (a corresponding forest plot will be subsequently produced for presentation/publication).

- To assess the effect of trial treatment and other clinicopathological variables on PFS, Cox proportional hazard models will be fitted.

- Initially a univariate (stratified and unstratified) Cox model will be fitted in the model and the statistical significance of trial treatment will be tested at the 5% significance level.
- o Subsequently, multivariate Cox models (stratified and unstratified) will be estimated, adjusted for the clinicopathological variables of interest as defined above (in case of unstratified model, the stratification factors will be also included in the covariates of the model). The backward elimination method, with a removal criterion at 10% will be used to conclude on the statistically significant variables of the model. The HRs along with the corresponding 95% CIs for all significant predictors (in the multivariate Cox model) will be summarized in a tabular format in the report (a corresponding forest plot will be subsequently produced for presentation/publication).
- The proportionality assumption of Cox model will be explored by Schoenfeld's residuals and by testing for time-dependent effect of covariates in extended Cox models. In cases that non-proportionality is detected further appropriate measures will be used
 - Use of variable(s), for which proportionality assumption is violated, as stratification factor(s)
 - Use of weighted tests, alternatives to log-rank for the comparison of survivals, such as the Wilcoxon test
 - Estimation of Restricted Mean Survival Time (RMST) at specific time points (close to median follow and covering the full follow-up time for the majority of patients)
 - Calculation of HR for separate time intervals

4 Additional secondary analysis

In this section, we present in detail the additional analysis that will be performed in the frame of final efficacy analysis for STIMULI trial.

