## 13. Response evaluation

### 13.1. RECIST 1.1 criteria

The patient's response to chemo-radiotherapy treatment and to nivolumab plus ipilimumab consolidation treatment will be assessed by RECIST 1.1 criteria (see appendix 2). Only patients with stable or responding disease will be eligible for randomisation. The response assessment according to RECIST 1.1 should be done by the local radiologist and reported on the eCRF.

For exploratory purposes, the response in the randomised nivolumab plus ipilimumab consolidation phase of the trial will also be assessed post-hoc centrally by immune-related response criteria based on RECIST 1.1.

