## **18.4. Evaluation of primary and secondary objectives**

The total study duration will be approximately 7.5 years including the 36 months recruitment period. The primary analyses on PFS and OS will be performed overall and stratified by radiotherapy schedule. An intent to treat primary efficacy analysis will be performed, including all eligible patients randomised (= efficacy cohort).

PFS and OS will be estimated by the Kaplan Meier method and compared between the two treatment arms by a stratified logrank test. In addition, stratified (by the randomisation stratification factors) and multivariate Cox models will be used for exploring the association of PFS and OS with treatment in the presence of prognostic factors.

The two treatment groups will also be compared with respect to secondary efficacy and tolerability endpoints. No multiplicity adjustment will be performed for these analyses.

Time to treatment failure (TTF) will be estimated by the Kaplan Meier method and compared between the two treatment arms based on the logrank test stratified by the randomisation stratification factors. Cox proportional hazards regression adjusting for prognostic factors will also be performed for this secondary endpoint.

All time-to-event endpoints will be presented and evaluated from date of randomisation, with secondary presentation from date of enrolment.

Clinical efficacy will be further described by objective response rate (ORR, defined as percentage of patients reaching a complete or partial response) based on RECIST 1.1 response

criteria. The determination of ORR will be restricted to patients who have not attained a CR during chemo-radiotherapy.

Assessment of response by immune-related response criteria based on RECIST 1.1 will be explored post-hoc, centrally, in the randomised consolidation phase of the trial.

Safety and the tolerability of the nivolumab plus ipilimumab consolidation therapy will be described by tabulation of the CTCAE Version 4 grade. The safety cohort will encompass all patients who have received at least 1 dose of IMP treatment plus all patients randomised to observation.

The correlation of biological markers with OS and PFS will be evaluated by univariate and multivariate Cox proportional hazards regression.

OS analysis will also be performed for the full cohort of 325 patients for descriptive purposes. The survival time for the full cohort will be defined as the time from enrolment into the trial until death.

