1.4 Statistical design, sample size and power

1.4.1 Based on protocol AM1

This is a 1:1 randomized phase II trial (stratified by twice-daily vs once-daily radiotherapy and PET-CT done vs not done) with co-primary endpoints PFS and OS. The **overall one-sided significance level of 0.05** is split to 0.**01 for PFS** and 0.**04 for OS**. A total of 325 patients are expected to be enrolled in 36 months of accrual time, leading to **260 patients randomized** to the two arms based on a 20% attrition rate due mainly to early progression events during the first 4 months after enrolment. An additional 3% loss to follow-up is assumed during the trial after randomization. A trial duration of 87 months is necessary for the **required 212 deaths** to be observed, while the main analysis of PFS will be performed when **148 PFS events** have occurred, which is expected at approximately 45 months. Using the log-rank test, the achieved power is 80% for PFS at the 45-months evaluation and 78% for OS at the end of the trial.

Median PFS and OS for the observation arm are expected to be 13.1 and 20.7 months, as measured of randomization. Taking into account that the patients randomized are of better prognosis than the total patients enrolled, the expected increase in medians for the cohort of patients in the experimental arm is 9.7 months and 9 months for PFS and OS respectively. This translated to a PFS HR of 0.57 and OS HR of 0.70.

The trial will end when either the total number of 212 deaths has been observed or at a maximum of 7.5 years from the first patient enrolment date.

Calculations are performed using the EAST package and simulations were run in the R statistical package.

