1.4.2 Modifications after premature accrual closure

Because of the low accrual rate as well as additional strategic considerations unrelated to the scientific rational of the trial design, trial's funding source (Bristol-Myers Squibb, BMS) informed ETOP on 18 March 2019 that cannot continue funding the STIMULI trial. Therefore, the Trial Steering Committee decided to close the accrual into the trial prematurely as of 30 April 2019. Note that no safety concerns led to the decision of accrual closing.

Patients who already consented were still allowed to be enrolled until 30 April 2019. After this date, no new patients would be allowed to be enrolled into the trial. Treatment and follow-up for

all included patients continued as per protocol. Patients in the chemoradiotherapy phase who meet the criteria, would be still allowed to be randomized.

Thus, taking into account the reduced number of randomized patients and the corresponding initially required events (148 PFS events, 212 OS events) which were not possible to be observed anymore, the statistical design was modified.

According to this latest statistical modification, the primary endpoint of the trial is now defined as only the PFS (previous: co-primary PFS and OS) using the overall one-sided significance level of 0.05 (previous: 0.04 for PFS and 0.01 for OS). The hypotheses for PFS remain the same (PFS HR=0.57, with 13.1 months median PFS assumed in the observation arm versus 22.8 in the experimental). In this setting, the number of the required PFS events, for testing the PFS hypothesis with 80% power, at 5% significance level, is 81 (in: 148 events).

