4.1 Patient accrual, balance of stratifications factors & baseline characteristics

- A consort diagram will be created to graphically depict the flow of patients and the phases of the trial.
- Patient accrual by center and country will be presented in tabular format (including enrolled, randomized and ineligible patients)
- For patients deemed ineligible a table summarizing the reasons for non-enrolment will be provided¹
- Observed vs. expected accrual over time will be graphically displayed.
- Balance of treatment allocation by center and by stratification factors will be summarized
- Patient and tumour baseline characteristics at enrolment (categorical: gender, smoking history, ECOG performance status at diagnosis, stage (based on 7th TNM classification), TNM stage and continuous: age at enrolment), will be presented for the full cohort of enrolled patients. The same characteristics will be presented for the cohort of randomized patients overall and separately by treatment arm. Note that the ECOG PS reported for the randomized patients is the PS recorded just before the randomization. Frequencies and corresponding percentages will be presented for categorical variables (if missing cases exist, a separate category named "Missing" will be created.), while the following descriptive measures will be considered for the continuous ones: n (non-missing sample size), mean, 95% CI for the mean, median, maximum and minimum values. Balance of baseline characteristics (at randomization) by treatment arm will be assessed via the Fisher's exact test for categorical variables and the Mann-Whitney U test for continuous.
- Available information on medical history will be summarised, by treatment arm.

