4.6 Descriptive analysis of the per-protocol cohort

For all patients enrolled under protocol AM1, irrespective of whether they were subsequently randomized or not, the following will be presented:

- Objective response to chemo-radiotherapy based on the tumour assessment performed before randomization.
- All reasons for non-randomization (included in section 4.2).
- OS analysis (KM plot, median OS, 1 and 2-year rates with 95% CIs) with start date the enrolment date, further adjusted for patients enrolled after the first chemotherapy cycle.

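### Response to chemo-radiotherapy, assessed before randomisation, is left out of the supportive PFS and OS models and the by-arm baseline table

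*SAP*

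**What the plan says.** **Response is collected before randomisation.** Protocol 16.4 requires a contrast-enhanced CT within 14 days before randomisation. Table 16 has a tumour-assessment form for it, and Protocol 14.3 uses an assessment at about week 15 to determine response to chemo-radiotherapy.

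**Response is already used.** Protocol 13.1: "Only patients with stable or responding disease will be eligible for randomisation". Protocol 18.4: "The determination of ORR will be restricted to patients who have not attained a CR during chemo-radiotherapy". SAP 2.2.2 and 4.3.3 repeat the ORR restriction.

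**The covariates do not include it.** SAP section 3 lists "gender, smoking history, ECOG performance status at randomization, stage of tumour, age (appropriately categorized) and biological markers (if available". The multivariate Cox models for PFS use this list with backward elimination at 10%, and the stratification factors enter as strata or covariates. SAP 4.3.1 uses the same variables for OS. Age therefore enters categorised, with no cut-points given.

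**Nor do the other lists.** The stratification factors are radiotherapy fractionation and PET-CT. SAP 4.4 repeats the section 3 variables and adds fractions per day. The baseline characteristics in SAP 4.1 are gender, smoking, ECOG status, stage, TNM and continuous age, and "The same characteristics will be presented for the cohort of randomized patients overall and separately by treatment arm".

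**Where response is reported.** SAP 4.6, for all patients enrolled under amendment 1 and with no split by arm stated: "Objective response to chemo-radiotherapy based on the tumour assessment performed before randomization".

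**The concern.** PFS and OS are counted from randomisation, after chemo-radiotherapy and PCI. The randomised patients are a mix of complete response, partial response and stable disease at that moment. SAP 4.1 accepts that status at time zero matters for ECOG, since it reports the value recorded just before randomisation. Disease status gets no such update: the only disease-extent covariate is stage.

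Accrual closed early, so the randomised cohort is smaller than the planned 260 and chance imbalances are larger. If the arms differ in response and response is prognostic, the unadjusted HR moves. The planned tables would not display the difference and the planned models could not correct for it.

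**Working it through.** **1. The plan's event count.** Inputs from the SAP: "This is a 1:1 randomized phase II trial" (1.4.1); "PFS HR=0.57, with 13.1 months median PFS assumed in the observation arm versus 22.8 in the experimental" (1.4.2); "Using 80% power and a one-sided type I error of 5%, a total of 81 PFS events are needed" (section 3).

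Schoenfeld, 1:1 allocation: events = 4(z₀.₉₅ + z₀.₈₀)² / (ln HR)².

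- HR = 13.1/22.8 = 0.5746: 4 × (1.645 + 0.842)² / 0.554² ≈ 80.5, so **81**, as stated.
- HR = 0.57: 79.

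This calculation contains no covariate, so nothing below changes it.

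**2. Chance of imbalance.** Assumptions not in the documents: N = 140-180 randomised; response share p = 20-50%. The SE of the difference in proportions between equal arms is √(4p(1−p)/N), and P(|d| ≥ 0.10) = 2[1 − Φ(0.10/SE)].

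| N | p = 0.20 | p = 0.35 | p = 0.50 |
|---|---|---|---|
| 140 | 14% | 21% | 24% |
| 160 | 11% | 18% | 21% |
| 180 | 9% | 16% | 18% |

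Example: N = 140, p = 0.50 gives SE = √(1/140) = 0.0845, z = 1.18, P = 24%.

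**3. Effect of a 10-point imbalance.** To first order the unadjusted HR is multiplied or divided by exp(d × ln g), where g is the assumed prognostic HR of the factor.

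| g | Factor at d = 0.10 | HR 0.57 becomes |
|---|---|---|
| 1.5 | 1.041 | 0.547 or 0.594 |
| 2.0 | 1.072 | 0.532 or 0.611 |
| 2.5 | 1.096 | 0.520 or 0.625 |

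**4. Power of the supportive Cox model.** Simulation: 1,500 trials per scenario, 150 randomised, exponential PFS, uniform entry, cut at the 81st event, treatment HR 0.57 conditional on response, one-sided 0.05. No age effect in this table.

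| Response share, g | HR without / with response | SE of log HR without / with | Power without / with |
|---|---|---|---|
| 20%, 1.5 | 0.573 / 0.569 | 0.228 / 0.229 | 79% / 79% |
| 35%, 2.0 | 0.582 / 0.569 | 0.228 / 0.229 | 77% / 80% |
| 50%, 2.5 | 0.595 / 0.567 | 0.227 / 0.229 | 75% / 80% |

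The Monte Carlo SE of one power figure is about √(0.8 × 0.2/1500) = 1 point. Adjustment does not reduce the SE of the log HR. The gain comes from removing attenuation of the HR.

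**5. Age.** With an assumed age HR of 1.3 per SD and response in the model, replacing dichotomised by continuous age moves power from 78.3% to 79.5%, 79.5% to 80.4% and 79.8% to 80.2% in the three scenarios: about 1 point or less.

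**The case against.** - **Imbalance is not wholly hidden.** SAP 4.2 reports the number randomised by arm and SAP 4.3.3 reports ORR by arm among patients without a prior complete response, so complete responders per arm can be found by subtraction. This stands. The split between partial response and stable disease still cannot be recovered, and nothing is tabulated, tested or adjusted.
- **The prognostic strength is assumed.** Protocol 4.2.3 itself calls radiological response after radiotherapy inaccurate, because post-radiation change cannot be told from tumour. The read is local and needs no confirmation (13.1, 13.4). This stands and points to the weaker end of the range, where the power gain is nil.
- **Marginal or conditional HR.** The design's 0.57 comes from arm medians, so it can be read as an unconditional effect. The unadjusted analysis then keeps its planned power. This stands for the word loss: on that reading adjustment is a gain over the plan and not the repair of a shortfall.
- **Response is not defined for everyone.** Evaluable, non-measurable disease is eligible (7.1.12), Table 15 allows a non-evaluable result, and it has no row for non-target disease alone. This stands, and the fix needs a category for it.
- **The models are exploratory.** The formal comparison is the stratified log-rank test. This is true and limits the point to the supportive analyses.

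A reader might also infer that categorising age hides an age imbalance. It does not: SAP 4.1 shows age by arm as continuous and tests it with Mann-Whitney.

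**Conclusion.** The omission is confirmed in SAP 3, 4.1, 4.3.1 and 4.4. A time-zero disease measure that the trial already collects and already uses for ORR is neither shown by arm nor available for adjustment.

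Its size is modest and depends on assumptions. With 140-180 randomised and a response share of 20-50%, an imbalance of 10 points or more occurs in about 9-24% of trials. It would shift the unadjusted HR by about 7% if the factor's HR is 2 (4-10% for 1.5-2.5). With 150 randomised, leaving the factor out costs the supportive models about 0-5 points of power through attenuation.

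Two stronger readings are not supported. One is that the plan loses precision: the SE of the log HR is essentially the same with and without response. The other is that the primary result is compromised: the stratified log-rank test and the 81 events stand as planned. The point is a nearly free improvement to the supportive analyses.

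**What to change.** 1. **SAP 4.1:** add response at the pre-randomisation CT to the by-arm baseline table for randomised patients. Use complete response versus not, or complete response / partial response / stable disease, with a category for non-evaluable or non-CR/non-PD results.
2. **SAP 3 and 4.3.1:** add the same variable to the pre-specified PFS and OS Cox covariates and exempt it from the 10% backward elimination, which could otherwise drop it.
3. **Minor:** enter age as continuous in these models and keep categories for the forest plot. This also removes the open choice of cut-points.

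Leave the primary test and event count as they are. A response subgroup is optional and would add one more comparison.

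The cost is SAP wording, since the data are already on the tumour-assessment form. The change should be made before the database download at 81 events, so that it cannot look data-driven. The small downside is one or two extra parameters in a supportive model with 81 events, plus one more if the non-evaluable category is populated.

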4.3 Secondary (efficacy) and exploratory endpoints

4.3.1 Overall survival

Similar to PFS the following will be presented for OS:

- Total number (%) of OS events, overall and by treatment arm (as well as by stratification factor)
- 1-year/2-year OS estimates, median and respective 95% CIs (comparison between treatment arms based on stratified and unstratified log-rank).
- Kaplan- Meier plot by treatment arm

- Subgroup analysis (number of events, median time and unstratified/unadjusted HRs (along with 95% CIs) and variables of interest)

- Univariate and multivariate Cox proportional hazards model, adjusted for the stratification factors and clinicopathological variables of interest; HRs and corresponding 95% CIs for all significant predictors will be presented in a table.
- Summary table of the death causes overall and by treatment arm (e.g., lung cancer, toxicity, other, etc)

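### The adjusted treatment hazard ratio for PFS and OS is tabulated only if significant, and subgroup consistency is assessed without any interaction estimate

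*SAP*

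**What the plan says.** **Multivariate models for PFS (SAP section 3, Further PFS analyses).** The Cox models have a stated aim: "To assess the effect of trial treatment and other clinicopathological variables on PFS". A treatment-only step comes first: "Initially a univariate (stratified and unstratified) Cox model will be fitted in the model and the statistical significance of trial treatment will be tested". Multivariate models follow, "adjusted for the clinicopathological variables of interest as defined above". That list covers sex, smoking, performance status, stage, age and, where available, biological markers; treatment is not on it. In the unstratified version the two stratification factors join the covariates. The selection rule is: "The backward elimination method, with a removal criterion at 10% will be used to conclude on the statistically significant variables of the model". The reporting rule is: "The HRs along with the corresponding 95% CIs for all significant predictors (in the multivariate Cox model) will be summarized in a tabular format". No sentence names a term that is exempt from removal, and none says that the adjusted treatment HR is shown whatever its p-value.

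**OS (SAP 4.3.1).** The reporting rule is repeated: "HRs and corresponding 95% CIs for all significant predictors will be presented in a table". No elimination step is stated; it could only be inferred from the remark that OS is handled like PFS.

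**Purpose in the protocol (18.4).** The multivariate models are for "exploring the association of PFS and OS with treatment in the presence of prognostic factors".

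**Subgroups (SAP 4.4).** The aim is to establish whether the treatment effect is consistent across pre-specified factors, for the primary and secondary efficacy endpoints. The plan is an estimate within each category, with HRs, 95% CIs and a forest plot for PFS. Neither the SAP nor protocol section 18 plans a treatment-by-factor interaction. Note 1 of SAP 4.4 refers to a multiple comparison adjustment that neither document defines.

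**The concern.** The multivariate model checks whether the treatment effect survives adjustment for prognostic factors. That check is useful only if its result is shown whichever way it falls. Under the SAP's table rule, the adjusted treatment HR appears when it is significant and may be missing when it is not. A reader of the final report could not tell a reassuring adjusted estimate from one chosen for display. An HR shown only when significant also overstates the effect on average.

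The rule also leaves two competent statisticians free to produce different tables from the same text. SAP section 5 requires independent reproduction by a second statistician, so the text should settle this.

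The subgroup gap is separate. The question in SAP 4.4 is how much the effect differs between categories. A list of within-category HRs does not state that quantity or its uncertainty.

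**Working it through.** **Inputs.** From the SAP: 81 PFS events, one-sided 5%, 80% power, medians of 13.1 and 22.8 months, PFS HR 0.57 (sections 1.4.2 and 3); 1:1 allocation (section 1.4.1); 10% removal criterion (section 3). Assumed: a two-sided Wald p-value for removal, exactly 81 events, and no correlation between covariates and treatment.

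**1. The plan's own figure.** Schoenfeld: events = 4(1.645 + 0.842)² / (ln HR)². With HR = 13.1/22.8 = 0.5746 this gives 81. With HR 0.57 it gives 79, and Freedman's formula gives 83. The stated 81 reproduces.

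**2. When the adjusted HR would be shown.** SE(ln HR) = 2/√81 = 0.222. The two-sided 10% cut is 1.645 × 0.222 = 0.366 on the log scale. So the estimate must be at or below exp(−0.366) = 0.69, or at or above exp(0.366) = 1.44.

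**3. How often it would be left out, and how much of that is new.** P(omitted) = P(|Z| < 1.645) with Z ~ N(|ln HR|/0.222, 1). The primary result is non-significant when Z < 1.645 in the direction of benefit, which is the same cut.

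| True HR | Adjusted HR omitted | Primary non-significant | Omitted although primary significant |
|---|---|---|---|
| 0.575 | 20% | 20% | 1.6–5.0% |
| 0.65 | 38% | 38% | 2.2–6.9% |
| 0.70 | 52% | 52% | 2.2–7.2% |
| 1.0 | 90% | 95% | not computed |

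The last column takes the primary and adjusted statistics as bivariate normal with equal means and a correlation of 0.99 down to 0.90. The documents give no correlation. Under these assumptions, 75–92% of omissions at HR 0.575, and 86–96% at 0.70, coincide with a non-significant primary result.

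**4. Effect of showing only significant values.** By simulation with the same SE, the geometric mean of the HRs that pass the cut is about 0.58 when the true HR is 0.70, and about 0.53 when it is 0.57.

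**5. OS.** No figure is given, because the SAP states no expected number of deaths after the redesign.

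**6. Precision of an interaction estimate for PFS.** SE(ln ratio of HRs) = √(4/d₁ + 4/d₂), where d₁ + d₂ = 81. Event splits are assumed.
- 50:50: √(4/40.5 + 4/40.5) = 0.444. The ratio detectable with 80% power at two-sided 5% is exp(2.802 × 0.444) = 3.5.
- 80:20: √(4/64.8 + 4/16.2) = 0.556, which gives a ratio of 4.7.

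Six or seven factors on four efficacy endpoints (PFS, OS, ORR, TTF) make 24 to 28 correlated tests. With no true interaction, 24 × 0.05 = 1.2 to 28 × 0.05 = 1.4 false positives are expected.

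**The case against.** The strongest reply is that treatment was never meant to be removable. The models exist to assess its effect, the covariate list omits it, and the protocol gives the same purpose. The lead-in to the list also says that these analyses "will also be performed and presented". This is the more natural reading, and it largely answers the question of retention. It does not answer the question of reporting: the table is still limited to significant predictors, so a retained but non-significant treatment term need not appear in it.

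A second reply is that little is lost. The unselected univariate HRs, both log-rank tests and the Kaplan–Meier curves remain. This stands and sets the severity. The omission rates in the working are also only approximate: adjusting for prognostic factors tends to move a Cox HR away from 1, which would lower them when there is an effect.

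Third, SAP 4.3.1 states no elimination for OS. This stands, and the OS fix should not introduce it.

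On subgroups, a reader can derive the ratio of HRs for a two-level factor from the two HRs and their CIs, and any interaction estimate will be imprecise. Both are true. But the SAP sets out to determine consistency and should report the quantity that addresses it. A reader might infer that the SAP judges consistency by whether each subgroup's CI excludes 1; it contains no such rule. A reader might also see a contradiction between Note 1 and the statement in protocol 18.4 that no multiplicity adjustment is made. That statement concerns the secondary endpoints, not PFS subgroups, so the defect is only that Note 1's adjustment is undefined.

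**Conclusion.** The point holds as a minor one, on supportive and exploratory analyses only. As written, the adjusted treatment HR for PFS and OS is tabulated only if significant. For PFS at 81 events, with an assumed two-sided 10% cut, that means an estimate of about 0.69 or less, or 1.44 or more. No interaction estimate supports the consistency aim in SAP 4.4.

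Three stronger readings do not follow. The documents do not say that treatment will be removed; their stated purpose points the other way. The 20–90% omission rates are not a new loss of that size, because most of them restate a non-significant primary result; the added part is roughly 2–7% at HRs of 0.575 to 0.70, under an assumed correlation. And the primary conclusion is not at risk: the formal test is the stratified log-rank test, so the type I error and the event target are untouched.

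**What to change.** **SAP section 3.** State that treatment and, in the unstratified model, both stratification factors are kept in every multivariate PFS model; that backward elimination at 10%, with its sides stated, applies to the other covariates only; and that the adjusted treatment HR with 95% CI is reported whatever its p-value.

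**SAP 4.3.1.** State that treatment is kept in the multivariate OS model and that its adjusted HR with 95% CI is reported whatever its p-value. Do not add an elimination step.

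**SAP 4.4.** For each listed factor add a treatment-by-factor interaction estimate: the ratio of effects with 95% CI, from a Cox model for PFS, OS and TTF and a logistic model for ORR. Add a global p-value for factors with more than two levels, such as stage. Label these exploratory, unadjusted for multiplicity and low-powered. Delete the reference in Note 1 to a multiple comparison adjustment, or define it.

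**Cost.** A sentence each in section 3 and 4.3.1 and a few lines of code for 4.4. No new data, and no change to the 81 events, the significance level or the primary test. The downside is imprecise interaction estimates and one or so chance finding among 24 to 28 tests, so they inform the question of consistency without settling it.
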